6.5.5 Microbiome Variables

Participants who are participating in the microbiome sub-study will be instructed to provide stool samples for metagenomic and metabolomic analysis on **Week -2 (Baseline Visit)**, **Week 4 (Mid-Tx 3 Visit)**, and **Week 8 (End of Treatment Visit after completing TN treatment)**. Changes in gut microbiome composition, as determined by metagenomics, will be derived by comparing the relative abundance of bacteria from baseline to weeks 4 and 8. Changes in neuroactive metabolites, as determined by metabolomics, will be derived by comparing levels from baseline to weeks 4 and 8. Although we have hypotheses involving specific metabolites, we chose an untargeted metabolomics approach to enable the identification of other biomarkers of importance.

CONFIDENTIAL

This material is the property of the University of Pennsylvania. Do not disclose or use except as authorized in writing by the study sponsor

6.5.6 Outcomes

Weight: Weight (primary outcome) will be measured by a physician's scale (pounds) at the beginning of every in-person visit. Participants will be wearing light clothing without shoes. Pre-cessation weight will be computed as the average of weights at the Intake and Baseline Visits prior to any change in smoking behavior. Weight change from Baseline to the 26-week follow-up will serve as a primary weight outcome variable.

Food Intake (24-Hour Dietary Recalls): Food intake (secondary outcome) will be assessed via 3 telephone-administered, 24-hour dietary recalls during the week after (or near) the Baseline, Mid-Treatment 3 (week 4), End of Treatment (week 8) and the 12-week and 26-week follow-up visits (n=15). A trained member of the research staff will use a multi-pass method with an interactive computerized software program, the ASA24® (Automated Self-Administered 24-hour Recall), to determine total kcal/day (outcome variable). The ASA24® was created by investigators at the NCI. Three recalls are considered optimal for assessing dietary intake, especially when weekend and weekdays are assessed, as we propose to do when possible. If participants are unable to complete a scheduled recall over the telephone or are onsite for a scheduled visit, participants may be asked to complete a 24-hour dietary recall with the research staff in-Center. Comparable accuracy can be achieved when administered in-person and over the telephone. Food recalls are widely used, reliable and valid, assessing kcals/day within 10% of actual dietary intake measured under laboratory observation and by doubly labeled water.

Changes in food intake (kcals) from baseline to week 12 will serve as an outcome for the microbiome sub-study.

Smoking Cessation (CO, Urine Cotinine, and Saliva Cotinine): Smoking abstinence (primary outcome) will be assessed and biochemically verified at EOT (week 8), at 12 and 26 weeks after the target quit date. The primary smoking outcome variable will be 7-day point prevalence abstinence (no smoking, not even a puff, for at least 7 days prior to the assessment) biochemically verified by CO < 5 ppm or Urine Cotinine assessment at a sensitivity of 100 ng/mL at EOT (week 8) and Follow-Up 1 and 2 visits (Week 12 and Week 26). Smoking status will also be biochemically confirmed by saliva cotinine < 15ng/ml at the 12- and 26-week follow-up.

Smoking Cessation will be assessed and biochemically verified at EOT (week 8) and at 12-weeks post TQD as a primary outcome for the microbiome sub-study. A reliable and valid timeline follow-back method is used to assess daily smoking (presence and rate). The smoking outcome variable is 7-day point prevalence abstinence biochemically verified by CO < 5 ppm or Urine Cotinine assessment at a sensitivity of 100 ng/mL at EOT (week 8) and Follow-Up 1 and 2 visits (Week 12 and Week 26). Smoking status will also be biochemically confirmed by saliva cotinine < 15ng/ml at the 12- and 26-week follow-up.

Smoking Rate Timeline Follow Back (TLFB): A reliable and valid timeline follow-back method will be used to assess daily smoking (presence and rate) at every visit post Intake.

fMRI Tasks *Neuroimaging Sub-Study Only: See section 6.2.12: fMRI Scanning Visits for the complete descriptions of the in-scanner tasks.

Food Cue-Induced Craving. The key outcome for this variable is BOLD signal change for most appetizing foods (versus water, and versus least appetizing foods as an active control). Primary regions of interest for the BOLD fMRI analysis are insula, caudate, OFC and ACC. As a secondary measure, food craving will be assessed prior to and after completion of the scan. The food craving assessment is the 3-item "desire" subscale of the reliable and valid state version of the Food Craving Questionnaire (FCQ-S).

CONFIDENTIAL

This material is the property of the University of Pennsylvania. Do not disclose or use except as authorized in writing by the study sponsor

Relative Reinforcing Value of Food (via Food Reward Reinforcement/Choice task). The primary behavioral outcome will be the amount of additional effort subjects are willing to expend in order to obtain food. The primary regions of interest for the BOLD fMRI analysis are VS and vmPFC. Within these regions, the food choices (all 50 trials where food is an option) vs. fixation will be the primary contrast. Selection of this primary contrast will ensure the same stimuli will be analyzed across participants and conditions and maximize statistical power for detecting food-related activation.

Working Memory N-Back Task. Based on our prior work, the primary performance measure will be correct reaction time, and the secondary measure will be number correct; the primary regions of interest for the BOLD analysis will be DLPFC and medial/frontal cingulate gyrus.

6.6 Tissue Specimens

Saliva: If a participant reports not smoking (not even a puff of a cigarette) for at least the 7 days prior to the 12-week and 26-week Follow-up Visits without the aid of NRT, the participant will be asked to provide a 5ml saliva sample used to assess cotinine levels and biochemically verify 7-day point prevalence abstinence.

Urine: A urine sample will be required at the Intake Visit, EOT Visit, Follow-Up 1 and 2 Visits, and both fMRI Scan Visits (neuroimaging sub-study only) for drug (~20-30ml), pregnancy , and cotinine screenings . These samples will be disposed of following the conclusion of the study visit.

Stool (microbiome sub-study only): Stool samples will be provided by participants at Week -2 (Baseline Visit), Week 4 (Mid-Tx 3 Visit), and Week 8 (End of Treatment Visit. See the Microbiome Sub-Study procedures for additional detail.

6.7 Sample Size Determination- Parent (Main) Study

For **Aim 1** we hypothesize that BAS+ vs. SC will have higher smoking abstinence rates and less PCWG at the 26-week follow-up (primary outcomes). Power calculations were all approximated as t-tests or z-tests, and conducted using PASS Software (Power and Sample Size, NCSS Software, Kaysville, UT), Bonferroni corrected for two primary outcomes ($p=.025$). Proportions of abstinent and smoking subjects will be compared using the log of the odds-ratio, which has a known variance. Informed by smoking cessation counseling plus TN research, we anticipate that the 6-month abstinence rate will be 13% in the SC (control) group and 25% in the BAS+ group (consistent with a persistent effect of BAS+ after the discontinuation of TN). A sample of 213 per group provides 82% power to detect this 12% difference in quit rates at 6 months. This represents a clinically meaningful effect and corresponds to a small effect size ($\delta=.15$). For PCWG, we will include all participants in the analysis, while testing a smoking status x treatment interaction. Informed by epidemiological and clinical studies of PCWG, we will have 80% power to detect a 6 pound (2.72 kg) difference in PCWG between BAS+ and SC, using the interaction term. We expect BAS+ vs. SC will have less post-cessation food intake (secondary outcome) at the 26-week follow-up. We have 80% power to detect a 320 kcal/day difference between the two groups ($p = .05$). In light of these considerations (i.e., 213 subjects per arm; total 426) and an attrition estimate of 15% across accrual, we will recruit a total of 245 subjects to each arm for a total of 490 subjects (~500).

For **Aim 2**, we hypothesize that BAS+ vs. SC, will increase alternative reinforcers, and reduce food reward, the RRVF, and food cue-induced craving. These changes, in turn, will predict less food intake and PCWG, and greater smoking abstinence at the 26-week follow-up. Using structural equation modeling, we will test the treatment effect on the slope of the mediators versus time, with pre-quit values representing the intercepts. We will examine the proportion of

CONFIDENTIAL

This material is the property of the University of Pennsylvania. Do not disclose or use except as authorized in writing by the study sponsor

treatment effect explained, and test with a delta method generated z-score (Type I error of .05). There are four proposed mediating pathways between treatment and outcome, so our Type I error will be corrected to 0.0125. For smoking abstinence, a sample of 426 gives us 80% power to detect small effects ($\delta=0.32$) for changes in the proposed mediators, where serial observations are uncorrelated within subject. This also applies to individual path strength. Even a modest within-subject correlation ($\rho=0.3$) provides 80% power to detect a small treatment effect ($\delta=0.20$). For PCWG, smoking status will be treated as a time-varying covariate, where changes in weight are represented as a slope factor (based on observed repeated measures of weight). With a sample of 426, we will have power to detect a small effect ($\delta < 0.20$), even without adjustment for within-subject correlation.

As an **exploratory aim**, we will test whether females, or participants with greater pre-treatment depression symptoms, or weight concerns, are more likely to experience PCWG and more likely to benefit from BAS+ vs. SC. We will test an interaction effect predicting that the effects of the BAS+ will be more pronounced for females, and for those who have greater depression symptoms, or weight concerns. For smoking abstinence, with a 6-month quit rate difference of 12% (25% BAS+ vs. 13% SC), we approximated power by simulation using a z-test based on the ratio of odds ratio (ORR). If this effect, for example, is completely derived from a larger effect of BAS+ among females (no effect in males), then we will have 80% power to detect an interaction with 213 subjects per treatment arm. This corresponds to an odds ratio of ~4.0 for a BAS+ effect in females and an odds ratio of 1.0 in males. All tests will be performed at a $p < .05$ significance level. We approximated the same interaction for PCWG using the z-score. Restricting the sample to abstinent participants (54 BAS+, 28 SC) with continuous moderators dichotomized at the median, a standard deviation of 3.5 kg, and a standard error of 1.63 for the interaction, we will have 80% power to detect an interaction difference of 4.7 kg (10.4 lbs.).

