The primary outcomes will be PCWG and 7-day point prevalence abstinence at 26 weeks after the target quit date. Food intake (secondary outcome) will be measured via 24-hour food recalls conducted over 3 consecutive days at pre-treatment, mid-treatment, end of treatment, and follow-up. Mediating mechanisms (e.g., alternative reinforcers, relative reinforcing value of food, food reward, and food cue-induced craving) will be assessed before, during, and at the end of treatment (week 8). Potential moderators include gender, depression symptoms and weight concerns.

1.2 *Background - Neuroimaging Sub-Study*

The parent randomized clinical trial of behavioral activation intervention (BAS+) integrates Behavioral Economic Theory and cognitive neuroscience research. The basic premise is that smoking cessation produces a reward dysregulation that increases the reward value of other reinforcers, such as highly palatable foods. Because food is a readily available reinforcer --and palatable foods increase in their incentive salience after quitting-- food cue-elicited reactivity in the brain's reward system would increase with smoking cessation. Food reward and reinforcing value also increases in the context of cessation leading to increased food intake. Cessation-induced increases in food reward are paralleled by decreases in the ability to control the consumption of palatable food. Research by our group and others shows that cessation impairs aspects of executive function that are critical to self-control. Abstinence reduces engagement of brain regions essential for cognitive control and individuals with lower levels of response inhibition are less able to resist palatable foods, and are more vulnerable to overeating. Working memory is important to keep goals in mind and for efficient use of behavior change tools, yet it can be depleted by efforts to manage cravings. This will be the first study to integrate these concepts and to explore brain mechanisms underlying a behavioral activation intervention (BAS+) to promote smoking cessation and mitigate PCWG.

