6.9 Sample Size Determination - Microbiome Sub-Study

Hypotheses will be tested at a global 5% Type 1 error rate (alpha) for each family of hypotheses, and we have chosen a completed sample (N=60) that will achieve at least 80% power using 2-sided tests. Our analysis of power is based on “effect size” (standard difference). We will control error in a family-wise manner, adjusting alpha using the Hochberg step up method for the number of tests within each hypothesis family. For **Aim 1**, we examined power using a preliminary longitudinal MANOVA to test for overall significance, and then examined the individual terms by bacteria or metabolite. If we have 12 to 18 taxa in our panel, we have 80% power for the overall test if two taxa make a 0.35-SD shift in abundance in response to smoking cessation. This assumes no within-subject correlation. Imposing a within subject correlation and using the jackknife variance estimate (clustered by subject) increases power. For follow-up testing, we will detect individual effects provided that at least one effect size exceeds ~ 1.3 .

Aim 2 examines whether the changes in the gut microbiome are associated with food intake and smoking abstinence at week 12. As with Aim 1, we will begin with the omnibus test using the multivariate pairwise distance measure (within subject) as a predictor. For the smoking outcome, we have 80% power to detect an odds ratio of 2.0, reflecting approximately a 20% difference resulting from a 1-SD change in pre-post distance. We also have 80% power to detect a correlation of 0.38, reflecting a 400 Kcal change in food intake. **Aim 3** begins with the model in Aim 2, above and explores interacting effects of treatment (BAS+ vs SC) on the relationship between gut microbiome changes, food intake and smoking abstinence. We will test an interaction effect predicting that the effects of gut microbiome changes (pre-post distance) on food intake and smoking abstinence will favor BAS+ versus SC. We have 80% power to detect a difference of 0.68 in the correlation of pre-post distance with food intake (0.68 versus 0), and a ratio of odds ratios (ORR) of 3.15, corresponding to a 25 to 30% greater change in abstinence for the BAS+ subjects.

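### Testing the two week-26 primary outcomes with Holm's procedure would keep the 5% family-wise error and add power at almost no cost; section 6.10 currently names no procedure

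*Combined protocol and SAP*

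**What the plan says.** Section 1.1 names two primary outcomes: "The primary outcomes will be PCWG and 7-day point prevalence abstinence at 26 weeks after the target quit date". Section 6.7 says its power calculations were "Bonferroni corrected for two primary outcomes", which gives 0.025 for each. For abstinence it states: "A sample of 213 per group provides 82% power to detect this 12% difference in quit rates at 6 months". For PCWG it states: "we will have 80% power to detect a 6 pound (2.72 kg) difference in PCWG between BAS+ and SC, using the interaction term".

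Section 6.10 tests the primary hypothesis by the z-score for treatment assignment, with week 26 as the primary time point. It gives neither a significance level nor a multiplicity procedure for the two primary tests. Holm is not mentioned anywhere.

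Other parts of the protocol use several methods:
- Parent Aim 2 divides alpha by four (0.0125).
- Neuroimaging Aims 1 and 2 use Bonferroni, and Aim 3 uses Hochberg (section 6.8).
- The microbiome sub-study controls error by "adjusting alpha using the Hochberg step up method for the number of tests within each hypothesis family" (section 6.9).

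**The concern.** Under fixed Bonferroni tests, each outcome must reach 0.025 whatever the other shows. Holm tests the smaller p-value at 0.025 and, if that is significant, the other at 0.05. It needs no assumption about how abstinence and weight gain are correlated, which matters because the documents give no correlation.

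Aim 1 hypothesises an effect on both outcomes, and the background presents the intervention as promoting cessation while limiting weight gain. The result that supports that account is success on both, and this is where fixed 0.025 tests give up most power. Because 6.10 names no rule, the choice is also still open in the analysis section, and it should be closed before the data are seen.

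**Working it through.** **Inputs.** From 6.7: 13% vs 25% abstinence, 213 per arm, log odds ratio z-test, alpha 0.025 per outcome, 80% power for PCWG. Assumed: two-sided tests (6.7 does not say for the parent study), the 80% for PCWG is at 0.025, and correlation 0 between the two test statistics, varied below. Critical values are 2.241 (0.025) and 1.960 (0.05).

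**1. The plan's own figure.** Pooled two-proportion test: (0.12·√213 − 2.241·√(2·0.19·0.81)) / √(0.13·0.87 + 0.25·0.75) = 0.926, and Φ(0.926) = 82.3%. The stated 82% reproduces.

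**2. The log odds scale named in 6.7.** ln[(0.25/0.75)/(0.13/0.87)] = 0.802. SE = √(1/53.25 + 1/159.75 + 1/27.69 + 1/185.31) = 0.258. The expected z is 3.11. Power is Φ(3.110 − 2.241) = 80.75% at 0.025 and Φ(3.110 − 1.960) = 87.5% at 0.05.

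**3. PCWG.** 80% power at 0.025 implies an expected z of 2.241 + 0.842 = 3.083. Power at 0.05 is then Φ(3.083 − 1.960) = 86.9%.

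**4. Holm with independent statistics.**
- Abstinence: 0.8075 + (0.8750 − 0.8075)·0.80 = 86.2%.
- PCWG: 0.80 + (0.8693 − 0.80)·0.8075 = 85.6%.
- Both: 0.8750·0.8693 − 0.0675·0.0693 = 75.6%, against 0.8075·0.80 = 64.6% under Bonferroni.
- At least one: 1 − 0.1925·0.20 = 96.2% under either rule, because Holm's first step is the Bonferroni test of the smaller p-value.

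**5. Error control.** With both nulls true, Holm errs exactly when Bonferroni does: 1 − 0.975² = 4.94% if independent, and at most 5% under any dependence. With one null true, an error requires that null's p-value to be at or below 0.05, so the bound is again 5%.

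**6. Only abstinence responds.** 0.8075 + 0.0675·0.025 = 80.9%, a gain of under 0.2 points.

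**7. Sensitivity.** Bivariate-normal simulation for power to show both:

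| Starting point | Correlation | Bonferroni | Holm |
|---|---|---|---|
| 80.75% and 80% | −0.3 | 62.6% | 74.7% |
| 80.75% and 80% | 0 | 64.6% | 75.6% |
| 80.75% and 80% | +0.3 | 67.2% | 77.0% |
| Stated 82% and 80% | +0.8 | 74.2% | 81.4% |

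If the 80% for PCWG was computed at 0.05, PCWG power at 0.025 is about 71% and Holm gives about 78%. Power for both then goes from about 58% to 70% (abstinence at 82%, correlation 0).

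**8. The current accrual target.** Section 4.2 aims for about 340, or 170 per arm. The SE becomes 0.289 and the expected z 2.779, so abstinence power is Φ(2.779 − 2.241) = 70.4% at 0.025 and 79.3% at 0.05. Scaling the PCWG statistic by √(170/213), an assumption, gives 2.754 and 69.6% power at 0.025. Holm for abstinence is 0.7044 + (0.7935 − 0.7044)·0.696 = 76.6%. Power for both rises from 0.7044·0.696 = 49% to about 62%.

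**The case against.** Bonferroni is valid and simple, and the plan reaches about 80% power or more under it at 213 per arm. It also pairs directly with 97.5% intervals. All of that stands, and no stated figure has to change because of this point.

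Bonferroni appears only in a sentence about power, so fixed 0.025 tests at analysis are an inference. That also stands, and it is why the fix belongs in 6.10.

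A reader might infer more than the documents support:
- *That the primary outcomes are singled out for the weakest method while the sub-studies use stepwise testing.* Bonferroni also governs neuroimaging Aims 1 and 2, and parent Aim 2 divides its alpha by four.
- *That both outcomes must succeed.* The documents call them primary and never co-primary. Splitting alpha fits a plan in which either can succeed, and there Holm leaves the chance of a positive trial unchanged.
- *That Bonferroni loses power on each outcome in all cases.* The loss is material only if both effects are real, and it shrinks at high correlation: about 7 points for both at 0.8.
- *That the stated 82% and 80% become conservative under Holm.* At 170 per arm Holm gives about 77% for abstinence, still below 82%.

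Holm has a real cost in reporting. If the second outcome has a p-value between 0.025 and 0.05, it is rejected although its 97.5% interval includes no effect.

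**Conclusion.** The point holds as an optional improvement, essentially free, together with a gap in 6.10 that needs filling in any case. It is not an error in the plan. At 213 per arm, with both effects as large as assumed and correlation 0, Holm adds about 5 to 6 points of power per outcome and 11 points for showing both. Family-wise error stays at or below 5%. The gain for both is about 10 to 12 points for correlations from −0.3 to +0.3. These figures rest on two-sided tests and on the PCWG power having been computed at 0.025.

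Holm does not replace reconciling the 426 in 6.7 with the target of about 340 in sections 3.4 and 4.2. At 170 per arm, abstinence power is about 70% under Bonferroni and 77% under Holm on the log odds scale. Holm cannot take it past the 79% of a full 0.05 test.

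**What to change.** Add to 6.10, and refer to it from 6.7:

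*The two week-26 primary outcomes are tested with Holm's procedure at two-sided family-wise 5%: the smaller p-value at 0.025 and, if significant, the other at 0.05.*

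In the same place, name the one PCWG test whose p-value enters the procedure. Section 6.7 powers PCWG on the smoking status by treatment interaction, whereas 6.10 refers both to the treatment z-score and to that interaction. Holm needs a single p-value per outcome.

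State how intervals will be reported, and note that a 97.5% interval may include no effect for an outcome rejected at the second step.

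The change adds no participants and loses no error control. Enrollment began in September 2016, so it should be a dated, justified amendment made before outcome data are seen. If that is no longer possible, 6.10 should state the fixed 0.025 tests that 6.7 implies. Keep the stated powers tied to 213 per arm until the sample size is reconciled.

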2.1 Parent (Main) Study

Aim 1: To evaluate the efficacy of BAS+ versus SC when delivered in conjunction with TN.

H1a: Compared to SC, participants in the BAS+ group will have less post-cessation food intake and gain less weight at week 26.

H1b: Compared to SC, participants in the BAS+ group will have higher smoking cessation rates at the end of treatment and at the 12- and 26-week follow-up time points.

Aim 2: To examine the mechanisms by which BAS+ reduces PCWG and promotes smoking cessation.

H2a: BAS+ vs. SC will increase engagement in and enjoyment from alternative reinforcers, and reduce the relative reinforcing value of food, food reward, and food cue-induced craving after smoking cessation.

H2b: Changes in these measures will predict reduced food intake and weight gain, which in turn will predict increased quit rates.

Exploratory Aim: We will explore whether women, or smokers with greater pre-treatment weight concerns or depression symptoms are more likely to exhibit PCWG and more likely to benefit from BAS+ vs. SC.

CONFIDENTIAL

This material is the property of the University of Pennsylvania. Do not disclose or use except as authorized in writing by the study sponsor

The proposed study breaks new conceptual and empirical ground by: (1) providing the first evaluation of the efficacy of BAS+ for smoking cessation and PCWG as an adjunct to the most widely used pharmacotherapy for smoking cessation and (2) examining the mechanisms by which BAS+ reduces food intake and weight gain. If the hypotheses are supported, the findings would suggest that targeting reward-related mechanisms common to both smoking and eating: (1) is an effective approach to promoting smoking cessation, while minimizing PCWG; and (2) is a viable approach for addressing two rewarding behaviors concurrently, without risking compensatory increases in one of those behaviors. Pretreatment assessments will enable the identification of potential individual differences in intervention efficacy.

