3.1 General Design - Parent (Main) Study

This is a randomized clinical trial of the efficacy of BAS+ plus TN compared to SC plus TN in treatment-seeking smokers. After completing an Intake Visit (~week -3), eligible smokers will be randomized (stratified by nicotine dependence, BMI and gender) to participate in 8 individual sessions of BAS+ or SC over a 10-week treatment period with two sessions prior to the target quit date (weeks -2, -1) and six sessions post-target quit date (TQD [week 0] and weeks 1, 2, 4, 6, and 8). Standard, 8-week; open-label TN will begin on the TQD. Moderators will be assessed pre-treatment. Mediating mechanisms will be assessed before, during, and at the end of treatment (EOT, week 8). Smoking will be assessed by self-report and biochemically confirmed (Carbon Monoxide [CO] < 5 or absence of Urine Cotinine) at all in-center visits (for CO ONLY) after quitting, at EOT (week 8), and at the 12- and 26-week follow-ups. Weight will be assessed at these same time points. Food intake will be measured by three consecutive days of 24-hour food recalls at Baseline [week -2] and 4-, 8-, and 12- and 26-weeks post-TQD. Smoking cessation and PCWG are the primary outcomes and food intake is a secondary outcome at 26-weeks post-TQD. Consistent with intent-to-treat (ITT) analyses, we will measure smoking cessation and weight gain in the full sample at the 26-week follow-up, evaluating a smoking status by treatment interaction for the PCWG analysis.

Time points (i.e. study weeks) displayed in Figure

[figure not shown]
CONFIDENTIAL

This material is the property of the University of Pennsylvania. Do not disclose or use except as authorized in writing by the study sponsor

1 and included within the Study Procedures Section represent approximations. Participants will follow a study schedule similar to that designated in Figure 1 and the Study Procedures, but will be permitted a degree of flexibility based on the maximum/minimum amount of time allowed between each time point established by the Principal Investigator. If a participant is unable to attend an in-person visit within the permissible window of time allotted between time points, counseling and applicable study measures may be completed/collected via telephone. In-person completion of the Intake and Baseline Visits are considered mandatory for study participation.

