preliminary analyses. Comparisons are all between-subjects. We will test for interaction between treatment and time point using the Wald Chi-square, and estimate a common odds-ratio across time points if they show no evidence of differing across time. The primary hypothesis will be tested using the z-score corresponding to treatment assignment at EOT, and at 12- and 26-weeks post quit, with the primary test of hypothesis 1a at 26-weeks post-TQD. Consistent with ITT analyses, we will measure smoking cessation and weight gain in the full sample at the 26-week follow-up, evaluating a smoking status (days x rate) by treatment interaction for the PCWG analysis (H.1.b.). The **exploratory aim** will evaluate variables that modify the effect of treatment on smoking cessation and PCWG. We will enter interaction terms (e.g., treatment x depression) to the models generated for Aim 1. The interactions will be retained if the z-score is significant ($p<0.05$). We will focus first on EOT, then the 12-week and 26-week follow-up time points, and finally the combined effect across time point.

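### The only Aim 1 power given for weight is for a smoking-status interaction, not for the between-arm difference that H1a states, and section 6.10's hypothesis labels leave the deciding weight test unclear

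*Combined protocol and SAP*

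**What the plan says.** All references are to the combined protocol and SAP.

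- Section 2.1 gives the weight hypothesis: "H1a: Compared to SC, participants in the BAS+ group will have less post-cessation food intake and gain less weight at week 26". It compares the arms, with no interaction and no restriction to quitters. The cessation hypothesis is separate: "H1b: Compared to SC, participants in the BAS+ group will have higher smoking cessation rates", at end of treatment, week 12 and week 26.
- Section 3.1 has everyone measured at week 26, "evaluating a smoking status by treatment interaction for the PCWG analysis".
- Section 6.7 splits alpha between the two primary outcomes (.025 each). For weight it says "we will include all participants in the analysis, while testing a smoking status x treatment interaction", and then gives the power: "we will have 80% power to detect a 6 pound (2.72 kg) difference in PCWG between BAS+ and SC, using the interaction term". It states no SD for this calculation and does not define smoking status. The other weight power statements in 6.7 concern Aim 2 mediation and the exploratory moderators.
- Section 6.10 says "The primary hypothesis will be tested using the z-score corresponding to treatment assignment at EOT, and at 12- and 26-weeks post quit", and continues "with the primary test of hypothesis 1a at 26-weeks post-TQD". Its next sentence describes the weight analysis as "evaluating a smoking status (days x rate) by treatment interaction for the PCWG analysis (H.1.b".

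**The concern.** Two things do not fit together.

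First, the powered quantity is not the hypothesised one. H1a asks whether BAS+ participants gain less weight than SC participants. The interaction asks whether the BAS+ effect differs by smoking status, a status that is reached after randomisation and that treatment is expected to change (13% versus 25% abstinent). One can be present without the other. Section 6.7 nevertheless describes the interaction figure as a difference between the two arms.

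Second, the labels in section 6.10 do not match section 2.1. Either the H.1.b. tag on the weight interaction is wrong, or 1a and 1b are swapped in both sentences. In the first case the treatment-assignment contrast decides H1a and has no stated power. In the second the interaction decides weight, and it does not test H1a as worded.

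Weight is one of two primary outcomes, and each .025 share of alpha needs one identified test.

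**Working it through.** **Inputs.** From section 6.7: 213 per arm (the number left after 15% attrition; 245 per arm are recruited), abstinence 25% BAS+ and 13% SC, alpha .025, target 2.72 kg. Assumed: two-sided testing; SD 3.5 kg, which section 6.7 states only for the exploratory moderator analysis among abstainers, with 5 and 7 kg as a range; and a binary abstinent/smoking split. Two-sided alpha .025 at 80% power gives z = 2.241 + 0.842 = 3.083.

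**Check of the setting.** For 13% versus 25% with 213 per arm, a two-proportion test at two-sided .025 gives 82.3%, against the stated 82%. At two-sided .05 it gives 88.7%. The assumed alpha and n are therefore consistent with the plan.

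**Reproducing the weight figure as an interaction.** Expected cell sizes are 53.25 and 27.69 abstinent, 159.75 and 185.31 smoking.

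- SE = 3.5 × √(1/53.25 + 1/27.69 + 1/159.75 + 1/185.31) = 0.903 kg
- Power = Φ(2.72/0.903 − 2.241) = 78.0%
- With section 6.7's rounded counts of 54 and 28 abstainers: SE 0.899 kg, power 78.4%, detectable difference 2.77 kg

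This is within about 2 points of the stated 80%.

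**Trying the same figure as the H1a contrast.** SE = SD × √(2/213). For 2.72 kg to have exactly 80% power, SD = 2.72 / (3.083 × √(2/213)) = 9.10 kg. The SD that gives exactly 80% for the interaction is 3.42 kg. The arithmetic agrees with the plan's own reference to the interaction term.

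**What the H1a contrast can detect (213 analysed per arm).**

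| Assumed SD (kg) | SE (kg) | Detectable at 80% = 3.083 × SE (kg) | Power for an overall 2.72 kg |
|---|---|---|---|
| 3.5 | 0.339 | 1.05 | over 99.9% |
| 5 | 0.485 | 1.49 | over 99.9% |
| 7 | 0.678 | 2.09 | Φ(4.01 − 2.241) = 96% |

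**Why one figure cannot stand in for the other.** Suppose BAS+ lowers gain by 2.72 kg in abstainers only, and SC abstainers gain G kg more than smokers (G is assumed; the documents give no value). The overall BAS+ minus SC difference is 0.25 × (G − 2.72) − 0.13 × G = 0.12G − 0.68 kg. The per-arm variances, including the mixing of abstainers and smokers, are SD² + 0.25 × 0.75 × (G − 2.72)² for BAS+ and SD² + 0.13 × 0.87 × G² for SC. At SD 3.5 kg:

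| G (kg) | Overall difference (kg) | SE (kg) | Power of the H1a contrast |
|---|---|---|---|
| 0 | −0.68 | 0.349 | 39% |
| 2 | −0.44 | 0.343 | 17% |
| 4 | −0.20 | 0.353 | 5% |

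In each row the interaction is the full 2.72 kg, with about 78% power if the within-group SD is 3.5 kg. Under a uniform 2.72 kg effect the interaction is zero and the H1a contrast is almost certain to succeed.

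**The case against.** The best defence is that section 6.10's treatment-assignment z-score was never the weight test. It follows a sentence about a common odds ratio, which belongs to the binary outcome. It is applied at end of treatment, week 12 and week 26, which are H1b's time points, whereas H1a names only week 26. Section 6.7 also introduces Aim 1 with abstinence first. On this reading 6.10 has simply swapped the labels, sections 3.1, 6.7 and 6.10 all name the interaction for weight, and the stated power matches the planned test.

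That reading is credible, and the documents do not exclude it. It does not rescue the plan. Both labels in 6.10 would then be wrong against section 2.1, and the deciding weight test would be one that does not test H1a as written. On either reading the 80% is not power for H1a.

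Three further points stand. The SD for the primary weight outcome is nowhere stated. The reconstruction cannot separate the interaction from an abstainers-only comparison, which reaches 80% at SD 3.77 kg; it is the plan's wording that settles this. Section 6.10 describes smoking status as days by rate, which is not the binary split used here, so 78% is a reconstruction.

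A reader might also infer that the wrong tag is there so that a test can be chosen once results are known. Nothing supports that: the interaction is pre-specified for weight in three sections. The fault is an ambiguity.

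**Conclusion.** The concern holds as a mismatch between the quantity powered and the hypothesis stated, with a labelling conflict that leaves the deciding weight test open. The mismatch rests on the wording of sections 2.1, 6.7 and 6.10 and needs no SD. The sizes depend on the assumed SD, two-sided testing and, for the interaction, the binary split.

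A reader might infer that H1a is underpowered. The documents do not support that. For an overall 2.72 kg difference the H1a contrast is very well powered across the SD range. The low figures (39%, 17%, 5%) need a benefit confined to abstainers, a borrowed SD and values of G that the documents do not give. They show that the two quantities are not interchangeable; they are not a forecast for the trial.

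Naming the deciding test and its power should be settled before analysis, because it concerns a primary outcome. The adherence terms in the models and the approximately 340 versus 426 sample sizes are separate matters and play no part in this conclusion.

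**What to change.** 1. Reconcile sections 2.1, 3.1, 6.7 and 6.10. Name the BAS+ versus SC contrast in week-26 weight change, from a model without smoking status, as the one test that decides H1a at alpha .025. Keep the interaction as supporting, with one definition of smoking status. Correct both hypothesis labels in 6.10 as needed: changing only the H.1.b. tag to H1a would leave two different tests carrying the same label. If the sponsor intends the interaction to decide, reword H1a to say so.
2. Replace the 80% for 2.72 kg with the detectable difference for the H1a contrast at 213 analysed per arm (245 recruited), two-sided alpha .025: 1.05, 1.49 and 2.09 kg at SD 3.5, 5 and 7 kg, with the SD stated as an assumption and its source given.
3. If the interaction power is kept, describe it as a difference of effects: about 78% for 2.72 kg at SD 3.5 kg, under a binary abstinent/smoking split.

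The cost is wording, the labels and one power line; visits and data collection do not change. The downside is dilution: if the benefit occurs only in abstainers, the overall contrast shrinks to 0.12G − 0.68 kg and may well miss it. A sponsor who expects that pattern should change H1a openly and not leave both readings in place.
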